5.4.8 Bleeding	
----------------	--

	Dose Modifications & Evaluations
Grade 1	Continue pazopanib at the current dose
	and monitor as clinically indicated.
Grade 2	1. Hold pazopanib until bleeding
	resolves to \leq Grade 1
	2. Restart pazopanib at a reduced
	dose; monitor as clinically
	indicated
Grade 3 or higher	Discontinue pazopanib permanently
OR	and remove from protocol therapy
Recurrent \geq Grade 2 event after dose	
interruption/reduction	

5.4.9 VascularThrombosis:

	Dose Modifications & Evaluations
Grade 2	Continue pazopanib at the current dose and monitor as clinically indicated.

Grade 3 (CVL associated only)	 Hold pazopanib Treat thrombosis according to institutional standards; would consider removal of the CVL. Resume pazopanib when all symptoms have resolved. If anticoagulation is required, use with caution.
All non-CVL associated Grade 3 AND all Grade 4	Discontinue pazopanib permanently and remove from protocol therapy

6

DRUG INFORMATION

In vitro studies demonstrated that pazopanib is metabolized by CYP3A4 with a minor contribution from CYP1A2 and CYP2C8. In vitro data also indicate that pazopanib is an inhibitor for CYP1A2, CYP2B6, CYP2C8, CYP2C9, CYP2C19, CYP2D6, CYP2E1,

and CYP3A4 with its most potent inhibition for the isoenzyme CYP2C9. In vivo, however, pazopanib is a weak inhibitor of CYP3A4, CYP2C8, and CYP2D6 with no effect on probes for CYP2C19, CYP2C9, and CYP1A2. Therefore, medications that are potent inducers or inhibitors of CYP3A4 are prohibited (refer to Section 4.8). Washout periods are specified in Sections 4.6, 4.7 and 4.8. If not specifically mentioned, it is at the discretion of the clinician based on the pharmacokinetic properties of each individual agent. Concomitant use of pazopanib with agents with narrow therapeutic windows that are metabolized by CYP3A4, CYP2C8, or CYP2D6 is not recommended. Coadministration may result in inhibition of the metabolism of these products and create the potential for serious adverse events.

In adults, pazopanib has a mean half-life of 30.9 hours after administration of the recommended dose of 800 mg. Elimination is primarily via feces with renal elimination accounting for <4% of the administered dose. Based on baseline hepatic function, 800 mg pazopanib is recommended for adult patients with mild impairment (defined as either normal bilirubin and any degree of alanine aminotransferase [ALT] elevation or as an elevation of bilirubin up to 1.5x upper limit of normal [ULN] regardless of the ALT value), and 200 mg for adult patients with moderate impairment (defined as an elevation of bilirubin >1.5 to 3xULN regardless of the ALT values). The maximum dose of pazopanib (200 mg) administered to adult patients with severe hepatic impairment did not achieve therapeutic plasma concentrations. Therefore, pazopanib is not recommended in adult patients with severe hepatic impairment (defined as total bilirubin >3xULN regardless of any level of ALT).

Pazopanib may cause prolongation of the QT interval and torsades de pointes. Refer to Appendix IIIB for agents to avoid during administration of pazopanib.

Pregnancy and lactation:

Pregnancy Category D

Pazopanib can cause fetal harm when administered to a pregnant woman. Based on its mechanism of action, pazopanib is expected to result in adverse reproductive effects. In pre-clinical studies in rats and rabbits, pazopanib was teratogenic, embryotoxic, fetotoxic, and abortifacient. In pre-clinical studies in rats and rabbits, pazopanib was teratogenic, embryotoxic, fetotoxic, and abortifacient. Administration of pazopanib to pregnant rats during organogenesis at a dose level of $\geq 3 \text{ mg/kg/day}$ (approximately 0.1 times the human clinical exposure based on AUC) resulted in teratogenic effects including cardiovascular malformations (retroesophageal subclavian artery, missing innominate artery, changes in the aortic arch) and incomplete or absent ossification. In addition, there was reduced fetal body weight, and pre- and post-implantation embryolethality in rats administered pazopanib at doses \geq 3 mg/kg/day. In rabbits, maternal toxicity (reduced food consumption, increased post-implantation loss, and abortion) was observed at doses ≥ 30 mg/kg/day (approximately 0.007 times the human clinical exposure). In addition, severe maternal body weight loss and 100% litter loss were observed at doses \geq 100 mg/kg/day (0.02 times the human clinical exposure), while fetal weight was reduced at doses ≥ 3 mg/kg/day (AUC not calculated).

There are no adequate and well-controlled studies of pazopanib in pregnant women. Protocol therapy should be immediately discontinued if pregnancy occurs while the patient is on therapy. Women of childbearing potential should be advised to avoid becoming pregnant while taking pazopanib and for up to 30 days after stopping pazopanib.

Excretion in breast milk unknown and breast-feeding while on pazopanib is not recommended.

Formulation and Stability:

Tablets

Pazopanib is supplied as a series of aqueous film-coated tablets containing, 200 mg, and 400 mg of the free base:

- 200 mg, oval-shaped, white, packaged in bottles containing 34 tablets each
- 400 mg, oval-shaped, white, packaged in bottles containing 68 tablets each

Tablet excipients in all tablet sizes include microcrystalline cellulose, povidone, sodium starch glycolate, and magnesium stearate. The film coating consists of titanium dioxide, hypromellose, polyethylene glycol, and polysorbate 80. Store the intact bottles at controlled room temperature (20°C-25°C). Excursions are permitted between 5°C and 25°C. Do not store pazopanib tablets above 25°C.

Pazopanib Suspension (to be prepared in pharmacies)

Pazopanib Powder for Oral Suspension is a white to slightly colored powder supplied to the clinical sites in amber glass (USP Type III) bottles with child-resistant closures. Each bottle contains 5 grams of pazopanib.

Pazopanib Powder for Oral Suspension should be reconstituted with 90 mL of sterilized or purified water to provide a white oral suspension containing 50 mg/mL of GW786034 as free base as detailed below.

- 1. Tap the sides to the bottle to loosen the powder.
- 2. Add 90 mL of room temperature sterilized or purified water for injection to the bottle.
- 3. Replace the cap tightly and shake vigorously by inversion for at least 2 minutes to ensure complete powder reconstitution.
- 4. Allow the bottle to sit for at least 3 minutes to allow any foam to dissipate. Suspension is then ready for use as a white, lemon-flavored, 50 mg/mL suspension.

Pazopanib oral suspension should be stored refrigerated ($2^{\circ}-8^{\circ}$ C). Do not freeze. The powder suspension is designed for multiple use and may be used for up to 35 days when refrigerated ($2^{\circ}-8^{\circ}$ C).

Guidelines for Administration: See Treatment and Dose Modification sections of the protocol. Also, see Appendix VII for Patient Instructions for Pazopanib suspension.

Pazopanib should be taken on an empty stomach at least 1 hour before or 2 hours after a meal. The tablets should be swallowed whole and cannot be crushed or broken.

Avoid concomitant strong CYP3A4 inhibitors as these may increase pazopanib concentrations. Avoid concomitant strong CYP3A4 inducers as these may decrease

pazopanib concentrations. Refer to Sections 4.5, 4.6, 4.7 and 4.8 for agents that should be avoided or used with caution. The consumption of grapefruit and its juice are not allowed for the duration of treatment with pazopanib. Concomitant use of pazopanib with agents with narrow therapeutic windows that are metabolized by CYP3A4, CYP2D6, or CYP2C8 is not recommended.

If a dose is missed, refer to section 4.1.4 Missed doses. If a patient vomits the dose, do not repeat the dose.

Dosing Instructions for Pazopanib (50mg/mL) multiple use oral powder suspension:

- Insert a Baxa 28 mm Press-In-Bottle Adapter (PIBA®) (these supplies will be provided to the site by Novartis) into the neck of the bottle. Check to ensure that the lip of the Adapter fits snugly with the top of the bottle.
- Swirl gently for at least 30 seconds to ensure homogeneity of the suspension immediately prior to the removal of the required dose for administration.
- Remove the required dose using a suitable graduated syringe (recommend Exacta- Med® Baxa) as follows:
 - 1. Ensure that the syringe plunger is fully pushed into the barrel.
 - 2. Insert the syringe tip into the Adapter, then invert the bottle and dispense at least 5 mL of suspension into the syringe and then pump the entire suspension back into the bottle to purge the syringe of any air bubbles. Repeat this step until the syringe is free from air bubbles.
 - 3. Withdraw the required dose. Then re-invert the bottle and remove the syringe from the Adapter and administer the dose as soon as possible.

Supplier:

Pazopanib suspension is supplied and distributed by Novartis.

Obtaining the Agent

Agent Ordering:

Sites will be provided the information for ordering drug supplies in the Study Procedures Manual.

Agent Accountability

The investigator is responsible for study medication accountability, reconciliation, and record maintenance. In accordance with local regulatory requirements, the investigator, designated site staff, or head of the medical institution (where applicable) must document the amount of Novartis investigational product dispensed and/or administered to study patients, the amount returned by study patients (if applicable), and the amount received from Sponsor and, when applicable, the amount returned to Novartis. Product accountability records must be maintained throughout the course of the study.

After completion of the study, a final inventory of accountability records and unused study medications will be performed by the study monitor and site personnel.

A record of the number of tablets dispensed to and returned by each patient at each visit must be maintained and reconciled with the study medication and compliance

records in the eCRF. At each site visit, the cause of any missed doses should be discussed and documented.

A record of the number of milligrams (determined by weight) of pazopanib in oral powder suspension dispensed to and returned by each patient at each visit must be maintained and reconciled with the study medication and compliance records in the eCRF. At each site visit, the cause of any missed doses should be discussed and documented.

After completion of the study, a final review of accountability records and inventory of unused study medications will be performed by the study monitor and site personnel. If the site has received documented approval from Sponsor, unused study medication may be destroyed, prior to inventory by the study monitor. In this case, the study monitor would review only study medication accountability records at the end of study visit. Additional information on the drug accountability process is provided in the Study Procedure Manual.

Any AE(s) associated with missed doses must be recorded in the eCRF. Patients should be instructed for the importance of compliance to study treatments.

Agent Destruction:

If allowed per site policy and procedures, unused study medications will be destroyed according to site-specific guidelines and proof of destruction will be forwarded to Novartis.

7

EVALUATIONS/MATERIAL AND DATA TO BE ACCESSIONED

Timing of protocol therapy administration, response assessment studies, and surgical interventions are based on schedules derived from the experimental design or on established standards of care. Minor unavoidable departures (up to 72 hours) from protocol directed therapy and/or disease evaluations (and up to 1 week for surgery) for valid clinical, patient and family logistical, or facility, procedure and/or anesthesia scheduling issues are acceptable (except where explicitly prohibited within the protocol). This policy does NOT apply to eligibility requirements; but to therapy and evaluations post consent and post the start of protocol-directed care. Novartis will not grant protocol waivers.

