- The sentence on "medications that increase gastric pH" is now updated to Proton Pump Inhibitors (PPI). This change is reflected in the protocol section on "Prohibited medications."
- To add anti-inflammatory and anti-platelet agents in the protocol section "Permitted medication to be used with caution". The use of these agents as a concomitant treatment should be monitored since pazopanib may result in an increase of blood pressure and bleeding episodes.
- To clarify that re-initiation of study treatment following hepatotoxicity requires approval from the Study Chair.
- To clarify that PK sampling is not required beyond Cycle 11 since it is unlikely that data beyond cycle 11 will provide any modification in the clinical pharmacology assessment of the study drug.
- To define the Per Protocol population and specify which analysis will be conducted in the different protocol defined datasets (Per Protocol Population and mITT population).

Changes to the protocol

Changes to specific sections of the protocol are shown in the track changes version of the protocol using strike through red font for deletions and red underline for insertions.

- Section 1.2: Added duration of response as secondary objective and clarified genotyping assessments.
- Section: 3.1.4: Clarified end of study criteria and addition of the option of closing recruitment of further patients in a given study cohort according to the efficacy results observed in two out of the three cohorts of primary interest at the end of stage 1.
- Section: 3.2.7: Update on the allowed timeframe for prior use of monoclonal antibodies.
- Section: 3.3.1: Updated timeframe for contraceptive requirements in females, and addition of contraceptive instructions for males with partners who can become pregnant.
- Section 3.3.2: Removed exclusion criterion regarding patients currently receiving antiinflammatory and anti-platelet agents.
- Section: 4.2: Clarification of criteria for starting subsequent cycles when no radiological tumor assessments are performed and alignment with safety management guidelines.
- Section: 4.5: Clarification of use of concomitant medications that increase gastric pH and addition of anti-inflammatory and anti-platelet agents in the protocol section of permitted medications to be used with caution.
- Section: 4.8: Change in the Prohibited Medications section, the reference of "medications that increase gastric pH" to "Proton Pump Inhibitors" (PPI).

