- Section: 5.4.3: Clarification regarding approval from Study Chair to re-initiate treatment following hepatotoxicity.
- Section 7.2.4: Updated timeframe for female use of adequate contraception to align with Investigator Brochure version 15.
- Section 7.3.2: Clarified that PK sampling schedule is not required beyond cycle 11.
- Section 9.3: Introduced the definition of Per Protocol (PP) population
- Section 9.4: Clarified data sets to be used for efficacy assessment, objective response analysis and all other efficacy analyses.
- Section 9.8.2: Addition of Duration of Response (DoR) as secondary objective.

IRBs/IECs

A copy of this amended protocol will be sent to the Institutional Review Board (IRBs)/Independent Ethics Committee (IECs) and Health Authorities.

The changes described in this amended protocol require IRB/IEC approval prior to implementation.

The changes herein affect the Informed Consent. Sites are required to update and submit for approval a revised Informed Consent that takes into account the changes described in this protocol amendment.

Summary of previous amendments

Amendment 4 (02-MAY-2016):

Amendment rationale

Subsequent to the acquisition of GlaxoSmithKline (GSK) compound GW786034, the purpose of this protocol Amendment 4 is to:

- Delete or replace references to GlaxoSmithKline or its staff with that of Novartis and its authorized agents to align with the change of sponsorship;
- Make administrative changes to align with Novartis processes and procedures;

As of 02-MAY-16:

18 patients have received study treatment in 1 country;

16 patients have discontinued study treatment.

The changes described in this amended protocol require Institutional Review Board (IRBs)/Independent Ethics Committee (IECs) approval prior to implementation.

A copy of this amended protocol will be sent to the IRBs/IECs and Health Authorities (HAs).

The changes herein affect the Informed Consent and all sites are required to update and submit for approval, a revised Informed Consent that takes into account the change of study sponsorship described in the protocol amendment.

Upon approval of this amendment, patients who have already been enrolled in the study will sign a new informed consent form indicating Novartis is the new study sponsor and continue the appropriate visit schedule.

Amendments 1 to 3

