3.3.1 Pregnancy or Breast Feeding/contraception

Pregnant or breast-feeding women are not eligible for this study due to risks of fetal and teratogenic adverse events as seen in animal/human studies. Negative

pregnancy tests must be obtained in girls who are post-menarchal. Females of reproductive potential may not participate unless they have agreed to use an effective contraceptive method beginning at the signing of the informed consent until at least 2 weeks after the last dose of the study drug. The definition of adequate contraception will be based on the judgment of the principal investigator or a designated associate. Study drug may also potentially be secreted in milk and therefore breastfeeding women are excluded. Males (including those who have had vasectomies) with partners who can become pregnant will need to use birth control while on this study, as will their partner. Men are advised to use condoms during sexual intercourse while on study drug and continue to use adequate contraception for at least 2 weeks after the last dose of protocol therapy.

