7.2.3 Cardiac Toxicity

Patients will have a baseline echocardiogram and EKG obtained pre-treatment, prior to Cycles 2 and 5, and then every 6 months (prior to Cycle 11, 17, etc) and as clinically indicated. See Section 5.4.6 for management of changes in left ventricular function and prolonged QTcB while on protocol therapy.

7.2.4 Pregnancy Testing and Reporting

The need for a screening pregnancy test depends on whether a female patient is of childbearing potential or non-childbearing potential. If a female patient is of childbearing potential, she must have a serum β -Human Chorionic Gonadotropin (β -HCG) pregnancy test performed within 7 days prior to the first dose of study treatment(s). Patients with a positive pregnancy test result must be excluded from the study. Patients with a negative pregnancy test result must agree to use an adequate contraception method as described below during the study until 2 weeks following the last dose of study treatment(s). Any pregnancy that occurs during study participation must be reported using a clinical trial pregnancy form. To ensure patient safety, each pregnancy must

be reported to Novartis within 24 hours of learning of its occurrence. Study treatment should be immediately discontinued if pregnancy occurs during study participation. The pregnancy must be followed up to determine outcome (including premature termination) and status of mother and child. Pregnancy complications and elective terminations for medical reasons must be reported as an AE or SAE (Section 11.8). Spontaneous abortions must be reported as an SAE.

Any SAE occurring in association with a pregnancy brought to the investigator's attention after the patient has completed the study and considered by the investigator as possibly related to the study treatment(s) must be promptly reported to Novartis.

Any SAE occurring as a result of a post-study pregnancy which is considered reasonably related to the study treatment by the investigator, will be reported to the Sponsor. While the investigator is not obligated to actively seek this information in former study participants, he or she may learn of an SAE through spontaneous reporting.

In addition, the investigator must attempt to collect pregnancy information on any female partners of male study subjects who become pregnant while the subject is enrolled in the study. Pregnancy information must be reported to Novartis as described above.

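### Section 7.2.4 ends required contraception 2 weeks after the last dose, while Section 6.1 advises avoiding pregnancy for up to 30 days

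*Protocol*

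**What the plan says.** Three places in the body of Amended Protocol Version 05 deal with the time after the last dose.

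- **Section 3.3.1** (exclusion criteria) lets females of reproductive potential take part only if they agree to an effective "contraceptive method beginning at the signing of the informed consent until at least 2 weeks after the last dose of the study drug". Men are advised to "continue to use adequate contraception for at least 2 weeks after the last dose of protocol therapy".
- **Section 7.2.4** (pregnancy testing and reporting) says that patients with a negative test must agree to adequate contraception "during the study until 2 weeks following the last dose of study treatment(s".
- **Section 6.1** (drug information, pregnancy and lactation) says: "Women of childbearing potential should be advised to avoid becoming pregnant while taking pazopanib and for up to 30 days after stopping pazopanib".

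Section 6.1 also gives the reason for caution: "In pre-clinical studies in rats and rabbits, pazopanib was teratogenic, embryotoxic, fetotoxic, and abortifacient". It adds that adequate controlled studies in pregnant women are lacking.

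The Amendment 5 list of changes has an entry for Section 3.3.1, "Updated timeframe for contraceptive requirements in females, and addition of contraceptive instructions for males with partners who can become pregnant", and one that reads "Section 7.2.4: Updated timeframe for female use of adequate contraception to align with Investigator Brochure version 15". It has no entry for Section 6.1.

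**The concern.** A site that counsels an adolescent from Section 7.2.4 would tell her that her obligation ends 2 weeks after the last dose. A site that counsels from Section 6.1 would advise her to avoid pregnancy for up to 30 days. Both statements are in force, and the protocol does not say that the advised period is meant to be longer than the required one, or why.

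The trial enrols patients up to 18 years of age and provides for post-menarchal girls. Section 6.1 states that the drug can harm a fetus. At stake is a clear and uniform safety instruction. The trial's statistical conclusions are not at issue.

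**Working it through.** The plan has no figure to reproduce, and no power, error-rate or sample-size formula applies. The check is a comparison of the three texts and one subtraction.

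**Inputs**

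| Place | Status of the text | Wording of the limit | In days |
|---|---|---|---|
| Section 3.3.1, females | condition of participation | "until at least 2 weeks after the last dose of the study drug" | 14 or more |
| Section 7.2.4, females | condition of participation | until 2 weeks | 14 |
| Section 6.1, women of childbearing potential | advice to be given | up to 30 days | at most 30 |

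**Conversion and gap**

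- 2 weeks × 7 = 14 days.
- 30 − 14 = 16 days. Because 6.1 states an upper limit, the gap is *up to* 16 days.

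**Pair by pair**

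1. *3.3.1 against 7.2.4.* The first is a minimum of 14 days and the second an end at 14 days. They agree on 14 days as the required length.
2. *3.3.1 against 6.1.* A minimum of 14 and a maximum of 30 do not exclude each other. A patient who continues to day 30 meets both.
3. *7.2.4 against 6.1.* Section 7.2.4 has no 'at least'. A patient who stops contraception on day 15 has done all that 7.2.4 asks, yet days 15 to 30 (16 days) may still lie inside the period advised in 6.1. This pair carries the inconsistency.

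**Where the difference may come from**

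The protocol appendices for Amendments 3 and 4 show that 3.3.1 and 7.2.4 formerly read 30 days, and that the 30-day sentence entered 6.1 with Amendment 3. Amendment 5 then lists changes to 3.3.1 and 7.2.4 only. That sequence is consistent with 6.1 not having been brought into line. The history is used here only to explain a possible origin; the inconsistency is among three passages of current text.

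**Number of patients**

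Section 9.10 projects 63 females among a maximum of 154 patients. The share who are post-menarchal is not given, so no count of affected patients can be derived.

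**The case against.** The strongest reply has several parts.

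- **The wording is partly compatible.** This stands for 3.3.1 against 6.1, as shown above. It does not help 7.2.4, which sets an end point.
- **The texts do different jobs.** Sections 3.3.1 and 7.2.4 are requirements, while 6.1 is counselling advice in a drug monograph. This is true and narrows the point. But sites may use all three, and nothing in the protocol explains a deliberate difference between the required and the advised period.
- **The animal data do not speak to the gap.** This stands. The exposure multiples in Section 6.1 come from dosing pregnant animals. They say nothing about residual exposure between day 14 and day 30 after stopping, so a reader who infers a demonstrated risk in that interval goes beyond the documents.

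Three other stronger readings are tempting.

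- A reader might infer that compliance with 3.3.1 cannot be judged. It can: 3.3.1 carries its own criterion and does not refer to 6.1.
- A reader might infer that the consent form can match only one of the texts. The consent pages were not available for this review, and a single stated period could satisfy both a minimum and a longer advisory limit.
- A reader might infer from the reference to the Investigator Brochure that 2 weeks is the right period and 6.1 is simply wrong. The brochure is not among the documents, and the change list shows only which sections were edited.

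**Conclusion.** The inconsistency is real and lies in current text, mainly between Section 7.2.4 and Section 6.1. Its size is up to 16 days for a patient who follows 7.2.4 exactly. The documents support saying that sites *may* counsel differently; they do not show that any site has done so or that any patient has been harmed.

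The conclusion rests on reading 7.2.4 as an end point rather than a minimum, and on treating the advice in 6.1 as something that sites act on. It takes no position on which period is correct.

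It is worth correcting because it concerns a safety instruction for a drug that the protocol says can cause fetal harm. It has no bearing on the primary endpoint, the two-stage decision rule, the sample size or any efficacy analysis. SAP Section 4.3 records a decision to terminate the study, which limits how many patients a correction could still reach.

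**What to change.** Reconcile Sections 3.3.1, 6.1 and 7.2.4 so that one post-treatment period is stated throughout, in the same form of words. If the sponsor intends the advised period to be longer than the required one, the protocol should say so and give the reason. Check the consent against the reconciled text. The sponsor decides the period; none is proposed here.

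The cost is a small text change and a letter to sites. The protocol's own description of Amendment 5 shows that such changes need IRB/IEC approval before they are implemented, so that step must be counted, together with a consent revision if the consent wording is affected. No analysis has to be rerun.
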